- Patients without regular internet access through a computer, tablet or smartphone are excluded.
- Subjects requiring long-term inpatient nursing care are excluded. For patients enrolled as inpatients, individuals being discharged to both home and acute rehab are eligible. Individuals being discharged to a skilled nursing facility or hospice are excluded.
- Expected life expectancy less than 6 months or other inability to comply with study follow-up.
- Pregnant women and prisoners are excluded

Vulnerable populations: Children, pregnant women, fetuses, neonates, and prisoners are not included in this research study.

Sample Size: 20 subjects will be enrolled.

Accrual: The comprehensive stroke center at the Hospital of the University of Pennsylvania (HUP) is a tertiary referral center for acute ischemic stroke, with annual case volumes of approximately 600 strokes per year on the inpatient stroke service. Additionally, the stroke team sees patients in the outpatient clinic both in follow-up from their acute hospitalization and in consultation to provide second opinions for patients treated elsewhere. Due to the broad inclusion criteria of this study, it is expected that many of the patients seen, both inpatient and outpatient, will be eligible for participation in this study. We expect that we will be able to enroll 1-2 patients per week and will complete enrollment within 6 months.

Recruitment: A stroke physician evaluates all patients with acute ischemic stroke who present to HUP. All stroke team physicians will be trained investigators in this study, and they will screen patients for eligibility during routine clinical care. Study physicians will also screen for potentially eligible subjects during outpatient clinic sessions. All eligible subjects will be informed of the study, and if they are interested in participation, a study physician will obtain informed consent. The original signed consent form will be kept in the study binder. A copy of

the signed consent form will be given to the patient and another copy will be placed in the medical record.

Procedures

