We will calculate the average PHQ-9 score at enrollment and 90 days. We will compare the PHQ-9 score from enrollment to day 90. The statistical power of this test is uncertain. In Table 2 we present estimated study power (with $\alpha=0.05$) across a range of assumptions about both the change in PHQ-9 over time and the standard deviation of the difference in PHQ-9 over time. These calculations show that although this is a small pilot study, we have >80% power to detect a difference in PHQ-9 of 3 or more points across a range of assumptions. The PHQ-9 will also be administered to subjects weekly via through the Joyable program. We will examine whether there are significant changes in score over time using repeated measures analysis (generalized estimating equations, GEE) with PHQ-9 score as the dependent variable and week as the independent variable.

In an exploratory analysis, we will divide patients into two groups based on PHQ-9 at study completion (*high depression symptoms*, defined as median or above and *low depression*

symptoms, defined as below the median score). Healthcare outcomes, including modified Rankin scale, health related quality of life, and healthcare utilization will be compared across groups. We hypothesize that patients with high depression symptoms will have worse functional outcome, lower quality of life, and higher healthcare utilization. We will also divide patients into groups based on their participation in the Joyable program and compare outcomes (e.g., PHQ-9 score, quality of life, health utilization) between subjects who showed high engagement in the program and those who showed low engagement.

Table 2. Statistical Power for single sample paired t-test

SD of the Difference	Difference in PHQ-9 Pre/Post Treatment				
	1	2	3	4	5
2	61%	99%	100%	100%	100%
3	32%	85%	99%	100%	100%
4	20%	61%	92%	99%	100%
5	15%	43%	77%	95%	99%
6	12%	32%	61%	85%	96%

Data Confidentiality

Internet-based files will only be made available to personnel involved in the study through the use of access privileges and passwords. Paper-based records will be kept in a locked, secure location and only accessible to study personnel. Prior to access to any study-related information, personnel will be required to sign statements agreeing to protect the security and confidentiality of identifiable information. Whenever feasible, identifiers will be removed from study-related information.

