b. Diabetes	No  Yes 
c. CAD	No  Yes 
d. Atrial Fibrillation	No  Yes 
e. CHF	No  Yes 
f. Prior TIA	No  Yes 
g. Prior Stroke	No  Yes 
h. Prior Anxiety	No  Yes 

- i. Prior Major Depressive Episode No Yes
- j. Prior PTSD No Yes
- l. Other (Please List):

11. **Tobacco** Never Former Current

12. **Current Alcohol** No Yes

If Yes, number of drinks per week: ___

13. **Marital Status:**

- Currently Married
- Divorced
- Widowed
- Never Married

14. **Number of People that you currently live with:** ___

15. **Were you working prior to this stroke?**

No Part Time Full Time

16. **Prior to the stroke, were you ever on a prescription medication for anxiety, depression, or PTSD?**

No Yes

If Yes, please list: _____

17. **Prior to the stroke did you ever participate in psychotherapy or counseling with a therapist?**

No Yes

18. **Stroke Location (check all that apply):**

- Right hemisphere
- Left hemisphere
- Posterior circulation
- Cortical
- Subcortical

19. **Vascular Territory of Stroke (check all that apply)**

ACA

- MCA
- PCA
- ICA
- Vertebral/Basilar

20. Stroke Etiology:

Free Text Description: _____

Stroke etiology at discharge (TOAST Criteria):

	Large Vessel Stenosis	
	Lacunar	
	Cryptogenic	
	Other: _____	

21. Discharge Disposition from Acute Hospitalization

Home
Acute Rehabilitation facility

22. Is the subject currently on pharmacotherapy for depression? (Review current medications)

- No
- Yes

If Yes, please list and select category from below: _____

- SSRI
- SNRI
- TCA
- Other

23. Abbreviated Duke Social Support Scale

Question	Answer		
Number of family members within 1 hour that you can depend on or feel close to?	None (1)	1-2 people (2)	More than 2 people (3)
Number of times in the past week in which you spent time with someone not living with you?	None (1)	1-2 times (2)	More than 2 times (3)

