 I am unable to wash or dress myself

Usual Activities (e.g. work, study, housework, family or leisure activities)

[figure not shown]
I have no problems with performing my usual activities
 I have some problems with performing my usual activities
 I am unable to perform my usual activities

Pain/Discomfort

I have no pain or discomfort
 I have moderate pain or discomfort
 I have extreme pain or discomfort

Anxiety/Depression

I am not anxious or depressed
 I am moderately anxious or depressed
 I am extremely anxious or depressed

YOUR HEALTH TODAY =

5. Healthcare Utilization

Since study enrollment:

How many times did you visit a **physician**? Do **not** include visits while in the hospital or to a hospital emergency room. Fill in with “0” or another number. _____ times

How many times did you go to a **hospital** emergency room? Fill in with “0” or another number. _____ times

How many different **times** did you stay in a hospital **overnight** or longer in the past 6 months? Fill in with “0” or another number. _____ times

How many total **nights** did you spend in the hospital? Fill in with “0” or another number. _____ nights

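### The Day-90 utilization form has no index-stay exclusion and two conflicting recall windows, so nights left in the index stroke admission count as healthcare use for patients enrolled as inpatients

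*Combined protocol and SAP*

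**What the plan says.** Healthcare utilization is a secondary outcome (Secondary Outcome variables), collected only at the 90-day visit (Table 1).

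- **Form.** In the Appendix, 90 Day Visit CRF, item 5, four questions stand under the heading "Since study enrollment": physician visits, emergency room trips, overnight stays and total nights. The nights question ("did you spend in the hospital? Fill in with" a number) has no window of its own. The stays question just above it asks about stays overnight "or longer in the past 6 months". The only exclusion is in the physician-visit question, where the subject is told not to "include visits while in the hospital or to a hospital emergency room".
- **Enrollment.** Exclusion Criteria: "For patients enrolled as inpatients, individuals being discharged to both home and acute rehab are eligible". Recruitment: "Study physicians will also screen for potentially eligible subjects during outpatient clinic sessions". The split between the two settings is not stated.
- **Follow-up.** The final visit is timed at 90 days, plus or minus 14, from enrollment rather than from discharge (90 Day In-person Visit).
- **Rehabilitation.** Baseline CRF item 21, "Discharge Disposition from Acute Hospitalization", offers home or an acute rehabilitation facility.
- **Analysis.** The Analysis Plan splits subjects at the median of end-of-study PHQ-9 and compares utilization, among other outcomes, as an exploratory analysis: "We hypothesize that patients with high depression symptoms will have worse functional outcome, lower quality of life, and higher healthcare utilization". Utilization is also to be compared by level of engagement. No adjustment is described for either comparison.

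**The concern.** For a subject enrolled in clinic, the utilization period starts at home. For a subject enrolled on the ward, it starts in a hospital bed. The second subject, answering as asked, reports at least one stay, plus whatever nights remained of an admission caused by the qualifying stroke. Those nights are not later use of care, and the program could not have affected whether the admission happened.

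Two things are at stake. The first is the reported level of utilization, which a pilot should supply in usable form for a later trial. The second is the comparison by Day-90 PHQ-9. If more severely affected patients stay longer and also score higher at Day 90, leftover index nights would collect in the high-symptom group, which is the direction the plan hypothesizes.

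**Working it through.** The plan gives no figure for utilization (no expected count, power or test), so there is nothing to reproduce. The point rests on the text. The numbers that follow only show its possible size.

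**1. Which nights fall in which window**

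| Subject | Nights, window from enrollment | Stays, six-month window |
|---|---|---|
| Enrolled during the index admission | Rest of index stay counts | Index stay counts |
| Outpatient, recently discharged | Index stay does not count | Index stay can count |
| Outpatient, remote stroke | Index stay does not count | Index stay does not count |

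The visit falls between 90 − 14 = 76 and 90 + 14 = 104 days after enrollment. Six months is about 183 days, so at Day 90 the stays question reaches 183 − 90 = 93 days before enrollment (79 to 107 days across the window). The two hospital questions can therefore treat the same outpatient differently. A subject who carries the six-month wording forward to the nights question would also add index nights from before enrollment.

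**2. Can the data be corrected afterward?** The baseline CRF records symptom onset and discharge destination. It has no index discharge date and no field for enrollment setting. Chart review might recover both, but the plan does not call for it.

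**3. Share of recorded nights (all inputs assumed)**

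Genuine later nights: 15% of 20 subjects admitted, 1 to 7 nights each (mean 4), giving 20 × 0.15 × 4 = 12.

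- *Larger case*: 8 inpatient enrollees with 3 index nights left, 8 × 3 = 24; of these, 4 go on to 14 rehabilitation nights, 4 × 14 = 56.
  - Rehabilitation not counted: 24 / (24 + 12) = 67%.
  - Rehabilitation counted: 80 / (80 + 12) = 87%.
- *Smaller case*: 4 inpatient enrollees with 2 nights left, 4 × 2 = 8; of these, 2 go on to 10 rehabilitation nights, 2 × 10 = 20.
  - Rehabilitation not counted: 8 / (8 + 12) = 40%.
  - Rehabilitation counted: 28 / (28 + 12) = 70%.

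**4. Effect on the PHQ-9 comparison (same inputs, simulated)**

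Genuine nights are unrelated to PHQ-9. Day-90 PHQ-9 has mean 7 and SD 4.5, with 3 points added for subjects who go to rehabilitation. The split is at the median, with 4,000 trials per case.

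| | High-PHQ-9 group has more nights: larger / smaller case | Two-sided Mann-Whitney rejection at 0.05 |
|---|---|---|
| Rehabilitation nights counted | about 80% / 72% | about 5–9% |
| Rehabilitation nights not counted | about 62% / 55% | about 5–6% |
| No PHQ-9 link | about 47–50% | about 4–5% |

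**5. A second model, with continuous severity (also assumed)**

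Here a mean of 3 index nights rises with severity, 50% or 100% of subjects are enrolled as inpatients, and severity correlates 0, 0.3 or 0.5 with PHQ-9. There are 10 subjects per group and 3,000 runs per scenario.

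- Index nights only, correlation 0.3 to 0.5: spurious difference 0.4 to 1.2 nights, rejection 5–14%.
- With about 14 rehabilitation nights also counted for the most severe 30% of inpatients: 1.5 to 5.0 nights, rejection 6–23%.
- Correlation 0: no systematic difference, rejection 4–5%.
- Post-discharge nights only: difference about 0, rejection about 2%.

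**The case against.** The strongest reply is that the text supports only a narrow point.

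- **Rehabilitation.** A reader might infer that rehabilitation nights are scored as hospital nights. The documents do not say so. The form asks about the hospital, and the baseline CRF treats acute rehabilitation as a destination after the acute hospitalization. Subjects may answer either way. This stands, and the large figures above depend on it.
- **False support for the hypothesis.** A reader might infer that the depression–utilization link will appear even if it does not exist. The 80% figure is only the chance that a raw difference has a given sign, against roughly 50% by luck. A test would seldom reject. The lean also needs severity to be related to both length of stay and Day-90 PHQ-9, and excluding aphasia, dementia and discharge to skilled nursing narrows the severity range. This stands too. The plan does itself predict worse function in the high-symptom group, so the link is plausible, but it remains an assumption.
- **Outpatients as a clean contrast.** A reader might infer that outpatients report zero index-related use. For the stays question as worded, that fails for anyone recently discharged.
- **Low consequence.** The comparisons are exploratory, in a 20-subject single-arm pilot. This is correct and limits the weight of the point.
- **Residual confounding.** Removing index nights does not remove confounding by severity, because sicker subjects may genuinely use more care later. This is also correct. The repair cures a measurement error, not the comparison.

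None of this answers the core point: remaining index nights count as the form is written, and its two windows disagree.

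**Conclusion.** The point holds as a measurement defect in a secondary outcome. Three facts are in the text: the heading starts the period at enrollment, enrollment may occur during the index admission, and no instruction removes the rest of that stay. The six-month wording in the stays question contradicts its heading, and the status of rehabilitation nights is undefined.

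Contamination of the level needs only that some subjects are enrolled before discharge. If none are, the nights question read under its heading is clean, though the stays question is still inconsistent. The size is unknown because the inpatient share and the remaining nights are not given; the 40% to 67% range is illustrative. Bias in the PHQ-9 comparison is conditional and modest if rehabilitation is not counted: about 0.4 to 1.2 nights in the severity model, and none without a severity–PHQ-9 link. The primary outcomes, activities completed and PHQ-9 change, are not touched. The change is worth making because it is nearly free and the forms shown do not capture what a later correction would need.

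**What to change.** On the 90 Day Visit CRF, item 5:

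1. Use one recall window for all four questions by deleting the six-month phrase from the stays question.
2. Instruct the subject not to count the hospital stay for the stroke during which they joined the study.
3. Record the discharge date of that stay and the enrollment setting (inpatient or outpatient).
4. Put inpatient rehabilitation nights on a separate line, so that they are neither mixed with hospital nights nor lost. Whether to add them to total use is then an open analytic choice.

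In the Analysis Plan, start each subject's utilization period at the later of enrollment and index discharge, and report visits, emergency room trips, stays and nights per 30 days at risk. For example, a subject with 3 index nights left who is seen at Day 90 contributes 90 − 3 = 87 days. The rate also handles the 76-to-104-day spread in visit timing. Show enrollment setting and baseline NIHSS beside the group comparisons.

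The cost is one instruction, one date and two short fields, a rate in place of a raw count, and a slightly shorter utilization period for inpatient enrollees.

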6. PHQ-9

PATIENT HEALTH QUESTIONNAIRE (PHQ-9)

NAME: _____ DATE: _____

Over the last 2 weeks, how often have you been
bothered by any of the following problems?
(use "✓" to indicate your answer)

	Not at all	Several days	More than half the days	Nearly every day
1. Little interest or pleasure in doing things	0	1	2	3
2. Feeling down, depressed, or hopeless	0	1	2	3
3. Trouble falling or staying asleep, or sleeping too much	0	1	2	3
4. Feeling tired or having little energy	0	1	2	3
5. Poor appetite or overeating	0	1	2	3
6. Feeling bad about yourself—or that you are a failure or have let yourself or your family down	0	1	2	3
7. Trouble concentrating on things, such as reading the newspaper or watching television	0	1	2	3
8. Moving or speaking so slowly that other people could have noticed. Or the opposite—being so fidgety or restless that you have been moving around a lot more than usual	0	1	2	3
9. Thoughts that you would be better off dead, or of hurting yourself	0	1	2	3

add columns + +

(Healthcare professional: For interpretation of TOTAL, TOTAL:
please refer to accompanying scoring card).

10. If you checked off *any* problems, how *difficult* have these problems made it for you to do your work, take care of things at home, or get along with other people?

Not difficult at all
Somewhat difficult
Very difficult
Extremely difficult

7. Semi-Quantitative Assessment of iCBT Program:

Was Joyable easy to use?

Extremely Difficult	Difficult	Neutral	Easy	Extremely Easy
1	2	3	4	5

How satisfied were you with Joyable activities?

Extremely Dissatisfied	Dissatisfied	Neutral	Satisfied	Extremely Satisfied
1	2	3	4	5

How satisfied were you with your Joyable coach?

Extremely Dissatisfied	Dissatisfied	Neutral	Satisfied	Extremely Satisfied
1	2	3	4	5

Was Joyable helpful with your home and/or work life?

Not Helpful	Slightly Helpful	Moderately Helpful	Very Helpful	Extremely Helpful
1	2	3	4	5

What did you like best about the Joyable program?

What about the Joyable program could be improved?

Would you recommend the program to other people with stroke?

Yes No

Why/Why Not?
